14.4.2. ANALYSIS OF EXPLORATORY EFFICACY VARIABLES

Unless otherwise specified, exploratory efficacy analyses will be performed between treatment group and placebo and based on FAS, mFAS (only for stage 1), and PPS. All results of these comparative analyses are used for exploratory purpose.

Document: Statistical Analysis Plan

Author: [name]

Version Number: 1.1

Version Date: 18Jan2023

Template No.: CS_TP_BS016 Revision 5

Reference: CS_WI_BS005

Effective Date: 01Apr2018

The change in IBDQ total and subscale scores at week 12 will be summarized by treatment group. The least square mean (LSMEANS), together with the p values and the 95% confidence intervals, between 0.2 mg vs. placebo and between 0.1 mg vs. placebo will be reported using the ANCOVA model (SAS PROC MIXED), with the stratification factor as the confounding factor in the ANCOVA model. The change from baseline over time on the IBDQ total and subscale scores will also be plotted by each treatment group for exploratory purpose. If the individual score is missing at week 12 or week 12 is out of visit window, the latest observation carried forward (LOCF) method will be applied. The latest record before week 12 will be used for imputation.

For the endpoint clinical response rate, clinical remission rate, mucosal healing rate, change in complete Mayo score and change in adapted Mayo score of stage 2 sub-study 1 will be same as secondary endpoint in stage 1. But for stage 2 sub-study 2 and 0.2mg only analysis, only descriptive statistics will be presented for single arm.

15. SAFETY ANALYSES

All safety analyses will be based on the SS by treatment group. Only the descriptive statistics will be reported on the safety endpoints and no statistical comparisons will be conducted on safety data, unless otherwise specified.

15.1. ADVERSE EVENTS

Adverse Events (AEs) will be coded using the Medical Dictionary for Regulatory Activities (MedDRA), version 21.1 or higher.

Treatment emergent adverse events (TEAEs) are defined as AEs that started, or worsened in severity, on or after the date of the first dose to the last dose date plus 28 days; it does not necessarily need to have a causal relationship with this treatment.

Missing date will be imputed following the blow rule:

Document: Statistical Analysis Plan

Author: [name]

Version Number: 1.1

Version Date: 18Jan2023

Template No.: CS_TP_BS016 Revision 5

Reference: CS_WI_BS005

Effective Date: 01Apr2018

When the AE start date is incomplete (i.e., partially missing), then the following rules will be applied:

Missing day and month

- If the year is the same as the year of the date of the treatment start date, then the day and month of the date of the treatment start date will be assigned to the missing fields.
- If the year is before the year of the treatment start date then December 31 will be assigned to the missing fields.
- If the year is after the year of the date of the treatment start date, then January 1 will be assigned to the missing fields.

Missing month only

- The day will be treated as missing and both month and day will be replaced according to the above procedure.

Missing day only

- If the month and year are the same as the month and year of the treatment start date, then the day of the treatment start date will be assigned to the missing day.
- If either the year is before the year of the date of the treatment start date or if both years are the same, but the month is before the month of the treatment start date, then the last day of the month will be assigned to the missing day.
- If either the year is after the year of the date of the treatment start date or if both years are the same, but the month is after the month of the treatment start date, then the first day of the month will be assigned to the missing day.

If the stop date is not missing and the start date is after the stop date after missing value calculation, the stop date will be used for the start date.

An overall summary table for all AEs will be provided by the count and percentage. An overall summary of number of subjects within each of the categories described in the sub-section below,

Document: Statistical Analysis Plan

Author: [name]

Version Number: 1.1

Version Date: 18Jan2023

Template No.: CS_TP_BS016 Revision 5

Reference: CS_WI_BS005

Effective Date: 01Apr2018

will be provided as specified in the templates.

Listings will include TEAEs and Non-TEAEs. TEAEs (Y/N) will be flagged in the listings.

15.1.1. ALL TEAEs

Incidence of TEAEs will be presented by SOC and PT and broken down further by maximum severity and relationship to study medication.

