Administration will be continued for 12 weeks. If subjects who complete 12 weeks of induction therapy of the stage 1 meet the criteria for the study stage 2, they can choose to enter it to further evaluate the safety and efficacy of CBP-307 in medium or long-term administration in subjects with moderate to severe UC. Subjects who early withdraw from the study or complete the study stage 1 but do not enter the stage 2 will enter a 4-week safety follow-up period.

[figure not shown]

Figure 4. Study design of the stage 1

Study stage 2

All subjects who complete 12 weeks of induction therapy (with CBP-307 or placebo) in the study stage 1 and complete all examinations (including colonoscopy) at the week 12 visit can choose to enter the study stage 2 of a total length of 40 weeks, including 36 weeks of continuous treatment and 4 weeks of safety follow-up after the last dose. Subjects who choose to enter the stage 2 will be required to sign an updated informed consent form and will be screened for eligibility.

The study stage 2 contains two sub-studies: sub-study 1 and sub-study 2. Subjects entering the study stage 2 will enter one of sub-studies based on their results of efficacy evaluation in the study stage 1 (Figure 5).

Sub-study 1 (subjects who have achieved clinical response by adapted Mayo score): Subjects who have clinical response shown by efficacy evaluation at week 12 in the study stage 1 and meet the eligibility criteria for stage 2 will enter sub-study 1 of the study stage 2 to receive double-blind maintenance treatment for 36 weeks (weeks 13 to 48), i.e., the therapeutic regimen for them in stage 1 will be continually maintained. Safety follow-up will be completed at 4 weeks after the last dose. Subjects who present with recurrent UC during maintenance treatment are required to terminate treatment and withdraw from the study.

For the subjects already enrolled as per the previous approved protocols (version 5.0 or earlier), they will follow the previous planned treatment in the sub-study 1 of stage 2 study.

UC disease recurrence i.e., an increased activity of UC, is defined as a repeated (occurring at 2 consecutive visits) partial Mayo score that is at least 5 points and is also ≥3 points higher than the score at week 12 (the end of induction therapy), and where the possibility of increased disease activity being due to other potential factors unrelated to UC can be excluded (e.g., infection, medication changes).

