Subjects will be screened at 1-21 days prior to the baseline visit. Administration will be continued for 12 weeks. At the same time, if subjects who complete 12 weeks of induction therapy in stage 1 study meet the criteria, they can be selected to enter stage 2 study to further evaluate the safety and efficacy of CBP-307 after medium or long-term administration in subjects with moderate to severe UC. 4 weeks of safety follow-up will be performed in subjects who complete stage 1 study but not enter stage 2 study or early withdraw from the study.

Stage 2:

All subjects who complete 12 weeks of induction therapy (with CBP-307 or placebo) in stage 1

Document: Statistical Analysis Plan

Author: [name]

Version Number: 1.1

Version Date: 18Jan2023

Template No.: CS_TP_BS016 Revision 5

Reference: CS_WI_BS005

Effective Date: 01Apr2018

study and complete all examinations (including colonoscopy) at visits week 12 can be selected to enter stage 2 for a total of 40 weeks, including 36 weeks of continuous administration and 4 weeks of safety follow-up after the last dose. Subjects selected to enter stage 2 will be required to sign an updated informed consent form and be rescreened for eligibility.

Stage 2 contains two sub-studies: sub-study 1 and sub-study 2. Subjects entering stage 2 will enter one of sub-studies based on their results of efficacy evaluation in stage 1.

Sub-study 1: Subjects who have **clinical response** shown by efficacy evaluation at week 12 in stage 1 and meet the eligibility criteria for stage 2 will enter sub-study 1 and continue on the double-blind maintenance treatment for 36 weeks (weeks 13 to 48), i.e., the therapeutic regimen for them in stage 1 study will be maintained. Safety follow-up is scheduled at 4 weeks after the last dose. Subjects who present with UC relapse during maintenance treatment period are required to terminate treatment and be withdrawn from the study.

Note: Patients previously enrolled by protocol 4.0/5.0 would have the chance to receive 0.1mg, then they will continue 0.1mg in stage 2 sub-study 1. But there is no 0.1 mg group in protocol version 6.0 now.

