6. GENERAL CONSIDERATIONS

Analysis results will be presented using descriptive statistics. For categorical variables, the number and percentage of subjects in each category will be presented; for continuous variables, the number of subjects [n], mean, standard deviation [SD] or standard error [SE], median, minimum, and maximum will be presented. Statistical comparisons will be tested at two-sided alpha of 0.05 significance level, unless otherwise specified. Data collected in the study will be presented in by-subject listings for all subjects in the full analysis set (efficacy analysis) and safety analysis set

Document: Statistical Analysis Plan

Author: [name]

Version Number: 1.1

Version Date: 18Jan2023

Template No.: CS_TP_BS016 Revision 5

Reference: CS_WI_BS005

Effective Date: 01Apr2018

(safety analysis), unless otherwise specified. All by subject listings will be presented by treatment group, subject identification number in ascending order, unless otherwise specified.

For stage 1 analysis, the analysis period for subjects who enroll stage 2 will be from screening (baseline visit) in stage 1 until before the first dose of stage 2. And for subjects who will not enroll stage 2 (including screen failed subjects before randomization, randomized subjects but not treated, and subjects early discontinued in stage 1), the analysis period will be from screening (baseline visit) in stage 1 until end of study in stage 1. For stage 2 sub-study 1 analysis, the full/safety analysis population will be the randomized subjects who receive at least one dose of study medication or placebo in stage 2, but the analysis period will be from screening (baseline visit) in stage 1 until the end of study in stage 2. But for subjects who will enroll stage 2 sub-study 2, the analysis period will be the date of first dose of the open-label CBP307 0.2mg in stage 2 until the end of study in stage 2 since treatment is changed to open-label CBP307 0.2 mg QD.

For 0.2mg (all stages) group, the analysis period will be the date of first dose of initial administration until the end of stage 2 study, including stage 2 sub-study 1 and stage 2 sub-stage 2.

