15.1.2. TEAEs LEADING TO DISCONTINUATION OF STUDY MEDICATION

TEAEs leading to permanent discontinuation of study medication will be identified by using the “Drug Withdrawal” to the item “Action Taken with Study Drug/ Placebo ” on the “Adverse Events” form of eCRF.

For TEAEs leading to discontinuation of study medication, summaries of incidence rates (frequencies and percentages) by SOC and PT will be prepared.

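### In sub-study 1, crude adverse event percentages take no account of the shorter follow-up in whichever arm relapses more

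*SAP*

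**What the plan says.** **Adverse event tables.** SAP 15.1.1: "Incidence of TEAEs will be presented by SOC and PT and broken down further by maximum severity and relationship to study medication". That sentence does not itself fix the scale, but two neighbouring ones do. SAP 15.1: "An overall summary table for all AEs will be provided by the count and percentage". SAP 15.1.2, on events leading to discontinuation: "summaries of incidence rates (frequencies and percentages) by SOC and PT will be prepared". So where the SAP speaks of incidence rates it means percentages of subjects. Under SAP 15 the tables are by treatment group on the safety set, and "Only the descriptive statistics will be reported on the safety endpoints and no statistical comparisons will be conducted on safety data".

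**Exit at relapse.** Protocol 5.1, sub-study 1: "Subjects who present with recurrent UC during maintenance treatment are required to terminate treatment and withdraw from the study". SAP 3.1 repeats the rule: "Subjects who present with UC relapse during maintenance treatment period are required to terminate treatment and be withdrawn from the study".

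**Time window.** SAP 15.1 counts events that start or worsen "on or after the date of the first dose to the last dose date plus 28 days". For sub-study 1, SAP 6 takes subjects dosed in stage 2, "but the analysis period will be from screening (baseline visit) in stage 1 until the end of study in stage 2".

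**What is absent.** Neither document plans a person-time denominator, an exposure-adjusted rate or a time-to-event summary for adverse events. SAP 12 summarises duration of exposure by treatment group, but separately from the adverse event tables.

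**The concern.** Exit from sub-study 1 depends on the outcome under study, and exit ends adverse event follow-up four weeks later. If one arm relapses less, its subjects are observed longer on average, and the chance of at least one recorded event grows with time observed. Two arms with the same event rate would then show different percentages.

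Medium- and long-term safety is a stated exploratory objective (SAP 2.3), and Protocol 5.2.1 gives reduced bias in the safety evaluation as one reason for keeping sub-study 1 blinded. Because no tests are planned on safety data, percentages side by side are the only between-arm display of adverse events a reader will have.

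**Working it through.** **The plan's own figures.** The plan states no relapse rate, event rate or expected size for sub-study 1, so there is nothing on this point to reproduce. Its one calculated figure, 52 per group for the stage 1 primary endpoint, does reproduce: 2 × (1.960 + 0.842)² × 2.0² / 1.2² = 43.6, so 44 evaluable, and 44 / 0.85 = 51.8, so 52. Nothing below depends on it.

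**Inputs from the documents**
- The period starts at stage 1 baseline (SAP 6), so a completer is at risk for 48 weeks of dosing plus 4, that is 52 weeks.
- A subject who leaves at week s is at risk for s + 4 weeks (SAP 15.1).
- Relapse needs two consecutive visits (SAP 3.1), and partial Mayo scores are due at weeks 18, 24, 32 and 40 (SAP 14.1). On scheduled visits, exit therefore falls at week 24, 32 or 40.

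**Assumptions.** Relapse is 40% in one arm and 15% in the other. The hazard is constant and the same in both arms at 1 event per patient-year, taking 52 weeks as a year. The true safety difference is therefore zero.

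**Formula.** For relapse proportion r, crude incidence = (1 − r) × C + r × R. Here C is the probability of at least one event in a completer and R the same for a relapser.

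C = 1 − exp(−52/52) = 0.632.

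*Exit midway through the 36 weeks* (week 30, window to week 34): R = 1 − exp(−34/52) = 0.480.

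*Exit split equally over weeks 24, 32 and 40* (windows 28, 36 and 44 weeks): R = (0.416 + 0.500 + 0.571) / 3 = 0.496.

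| Exit pattern | Relapse | Crude incidence | Gap (points) |
|---|---|---|---|
| Midway | 40% vs 15% | 57.1% vs 60.9% | 3.8 |
| Weeks 24, 32, 40 | 40% vs 15% | 57.8% vs 61.2% | 3.4 |
| Midway | 30% vs 15% | 58.6% vs 60.9% | 2.3 |
| Midway | 50% vs 20% | 55.6% vs 60.2% | 4.6 |
| Either | equal | equal | 0 |

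The gap is the difference in relapse times (C − R). For the first row: 0.25 × (0.632 − 0.480) = 0.038.

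**A less common event.** With a 10% risk over 52 weeks, relapse of 20% vs 50% and exits at weeks 24, 32 and 40, the percentages are 9.4% vs 8.5%. That is 0.9 points, in an arm observed for a mean of 48.8 weeks against 44.0.

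**After the fix.** With a constant hazard λ, mean time to first event or end of window equals crude incidence divided by λ. In the first row, the arm with 40% relapse has 0.571 subjects with an event over 0.571 patient-years, and the other arm has 0.609 over 0.609. Both give 100 per 100 patient-years, so the spurious gap disappears.

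**The case against.** **The effect is small against the noise.** Sub-study 1 takes only week 12 responders who opt in. If 20 to 30 per arm enter (an assumption), 3.8 points is about one subject (0.038 × 20 = 0.8; 0.038 × 30 = 1.1). The standard error of the difference is √[(0.571 × 0.429 + 0.609 × 0.391) / n], or 13 to 16 points, and about 10 points even with all 52 per arm. This stands, and it limits how much weight the point can bear.

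**Unequal follow-up will be visible.** SAP 12 tabulates exposure by arm, SAP 8 tabulates discontinuation reasons, and listings carry study day. Stage 2 is exploratory with no alpha (Protocol 9.13). All true, but the exposure table gives dosing time rather than the adverse event window. A reader cannot rebuild time to first event for each event category from it. It discloses the imbalance without correcting the comparison.

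**The direction is not certain.** This also stands. Protocol 8.1.1 counts exacerbation of pre-existing disease as an adverse event, so UC worsening would add events to the arm that relapses more. Sub-study 1 has no second titration (Protocol 6.2), so events at titration fall in stage 1, before differential exit can act.

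**Stronger readings the documents do not support**
- *A gap of about 5 points.* A reader who counted only the 36 maintenance weeks would get 41.7% vs 46.9%. SAP 6 starts the period at stage 1 baseline, and the 28-day tail also counts. Both dilute the effect.
- *The drug will look less safe.* The documents do not say which arm will relapse less, and the result needs similar hazards in the arms.
- *The same bias in sub-study 2 and the 0.2 mg all-stages set.* These are treated as single-arm (SAP 14.4.2). Exit of non-responders at week 24 mixes follow-up lengths there, but there is no between-arm comparison to distort.

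**Conclusion.** The point holds conditionally, for sub-study 1 only. If relapse differs between arms and event hazards are otherwise similar, crude percentages overstate adverse events in the arm that relapses less. With 40% vs 15% relapse and one event per patient-year, the overstatement is 3.4 to 3.8 points over the SAP's analysis period. With midway exit it runs from 2.3 to 4.6 points for relapse of 30% vs 15% to 50% vs 20%. Uncommon events are shifted by less in absolute terms. All relapse and event rates here are assumed. No primary or confirmatory conclusion is affected. This is a cheap improvement to an exploratory safety display.

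**What to change.** In SAP 15.1, for sub-study 1, keep the percentages and add beside them the number of subjects with at least one event per 100 patient-years. Count time from first dose to the first event or the end of the treatment-emergent window, whichever comes first, and show patient-years per arm. Apply this to all TEAEs, SAEs, TEAEs of grade 3 or higher, and adverse events of special interest.

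The percentages should stay because a rate assumes a roughly constant hazard. For events concentrated at titration, longer event-free follow-up dilutes the rate.

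For sub-study 2 and the 0.2 mg all-stages set the same display is an optional aid to interpretation. SAP 5.3 defines no safety set for all stages, so that would need settling first.

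Cost: modest extra programming, since time to first event must be derived for each category. Adverse event start dates and first and last dose dates are already collected. Rates for rare events will be imprecise.

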15.1.1.1. Severity

Severity is classed per CTCAE grade. If a subject report a TEAE more than once within that SOC/PT, the AE with the worst-case severity will be used in the corresponding severity summaries.

15.1.1.2. Relationship to Study Medication

Relationship, as indicated by the Investigator, is classed as “Related”, “Possibly Related”, “Unlikely Related”, “Not Related”, A “Related” TEAE is defined as a TEAE with a relationship to study medication as “Related”, “Possibly Related” to study medication. TEAEs with a missing relationship to study medication will be regarded as “Related” to study medication. If a subject report the same AE more than once within that SOC/ PT, the AE with the worst-case relationship to study medication will be used in the corresponding relationship summaries.

15.1.2. TEAEs LEADING TO DISCONTINUATION OF STUDY MEDICATION

TEAEs leading to permanent discontinuation of study medication will be identified by using the “Drug Withdrawal” to the item “Action Taken with Study Drug/ Placebo ” on the “Adverse Events” form of eCRF.

For TEAEs leading to discontinuation of study medication, summaries of incidence rates (frequencies and percentages) by SOC and PT will be prepared.

15.1.3. SERIOUS ADVERSE EVENTS

Serious adverse events (SAEs) are those events recorded as “Yes” to the item “Serious Event?” on

Document: Statistical Analysis Plan

Author: [name]

Version Number: 1.1

Version Date: 18Jan2023

Template No.: CS_TP_BS016 Revision 5

Reference: CS_WI_BS005

Effective Date: 01Apr2018

the adverse events page of the (e)CRF. A summary of serious TEAEs by SOC and PT will be presented.

15.1.4. ADVERSE EVENTS LEADING TO DEATH

TEAEs leading to Death are those events which are recorded as "Fatal" to the item "Outcome" on the Adverse Events page of the (e)CRF. A summary of TEAEs leading to death by SOC and PT will be presented.

15.1.5. ADVERSE EVENTS OF SPECIAL INTEREST

Adverse events of special interest are those events which are recorded as "Yes" to the item "Is This an Adverse Event of Special Interest?" on the Adverse Events page of the eCRF. The adverse event of special interest will include the following:

- Bradycardia and cardiac conduction abnormalities
- Pulmonary toxicity
- Hepatotoxicity
- Macular Edema
- Opportunistic or serious infections
- Malignant neoplasm of skin
- Posterior reversible encephalopathy syndrome
- Progressive multifocal leukoencephalopathy.

A summary of adverse event of special interest by SOC and PT will be presented.

15.2. DEATHS

If any subjects die during the study as recorded on the "death" page of the eCRF, the information will be presented in a summary table and a data listing.

Document: Statistical Analysis Plan

Author: [name]

Version Number: 1.1

Version Date: 18Jan2023

Template No.: CS_TP_BS016 Revision 5

Reference: CS_WI_BS005

Effective Date: 01Apr2018

15.3. LABORATORY EVALUATIONS

Laboratory tests include the following: Laboratory test item	Parameter
Hematology	Red blood cell (RBC) count, HGB, hematocrit (HCT), white blood cell count, blood platelet count, leukocyte differential count (lymphocyte count, neutrophil count, monocyte count, eosinophil count, basophil count)
Blood biochemistry	
Liver function test	Total bilirubin, conjugated bilirubin, ALT, AST, γ -GT, alkaline phosphatase, albumin, total protein, lactate dehydrogenase
Kidney function test	Urea, creatinine, uric acid, Na, K, Cl, Ca, P, amylase ¹
Blood glucose examination	Fasting blood glucose (FBG)
Fasting blood fat ²	Total cholesterol, low-density lipoprotein cholesterol, high-density lipoprotein cholesterol and triglycerides
Coagulation	Prothrombin time activated partial thromboplastin time, and international normalized ratio
Urinalysis/microscopy ³	Specific gravity, pH, nitrite, protein, glucose, ketone bodies, urobilinogen, bilirubin, occult blood, esterase leukocyte/erythrocyte, and

Document: Statistical Analysis Plan

Author: [name]

Version Number: 1.1

Version Date: 18Jan2023

Template No.: CS_TP_BS016 Revision 5

Reference: CS_WI_BS005

Effective Date: 01Apr2018

	white blood cells
Fecal culture/microscopy⁴	Fecal culture, C.difficile, eggs and parasites, and fecal calprotectin
Others	
Virological and serological tests	Anti-VZV IgG, HIV antibody, HBsAg, HBsAb, HBcAb and HCVAb
	Syphilis antibody
	HBV DNA, HCV viral loads
Detection of immunoglobulin	Immunoglobulin A, G, M
Detection of C-reactive protein	C-reactive protein
Pregnancy test ⁵	Blood β -human chorionic gonadotropin and urine pregnancy test
Quantiferon or Quantiferon Plus test ⁶	TB

Abbreviations: ALT=alanine aminotransferase; AST=aspartate aminotransferase; γ -GT= γ -glutamyltransferase; HBcAb=hepatitis B core antibody; HBsAb=hepatitis B surface antibody; HBsAg=hepatitis B surface antigen; HCVAb=hepatitis C antibody; HIV=human immunodeficiency virus; IgG=immunoglobulin G; TB=tuberculosis; VZV=varicella zoster virus.

1. Abnormal laboratory parameters or potential medical condition inconsistent with the clinical manifestations of UC should be repeatedly measured. At any follow-up after drug administration, if the amylase level is significantly higher than the clinical reference range (≥ 300 U/L), the lipase level should be measured to determine the source of elevated amylase (outside the pancreas).
2. Subjects must fast within 9 hours before a laboratory test.
3. If urinalysis show occult blood or abnormal urine protein in subjects' urine samples, a microscopy needs to be performed. A microscopy mainly refers to a blood test that measures

Document: Statistical Analysis Plan

Author: [name]

Version Number: 1.1

Version Date: 18Jan2023

Template No.: CS_TP_BS016 Revision 5

Reference: CS_WI_BS005

Effective Date: 01Apr2018

white blood cells and red blood cells. All other tests are tests with test strips.

4. Fecal culture/microscopy (involving fecal culture, C.difficile, eggs and parasites) is required to be performed at screening. During the screening period and any time point during the study if the subject has symptoms including aggravation of the disease condition or disease activity before recovery, stool samples can be collected for fecal culture/microscopy and C.difficile analysis.
5. Women with fertility are required to undergo a pregnancy test (involving blood β -human chorionic gonadotropin and urine pregnancy test). At screening, subjects with amenorrhea for <5 years are required to undergo measurement of follicle stimulating hormone to confirm postmenopausal condition.
6. Subjects can be enrolled in the study if it is evidenced that TB was treated successfully and Quantiferon or Quantiferon Plus test result is negative. If Quantiferon or Quantiferon Plus test result was uncertain at screening, the retest may be carried out during screening period. If Quantiferon or Quantiferon Plus retest result was uncertain, the subject should not participate in the study. If Quantiferon or Quantiferon Plus retest result is negative, the subject can be enrolled in the study.

Hematology, blood chemistry, and coagulation test results will be summarized at each study visit by treatment group.

Subjects with abnormalities in hematology assessments, defined as absolute lymphocyte count (ALC) <200 cells/uL, absolute neutrophil count (ANC) < 500 cells/uL as well as ANC <1000 cells/uL and total WBC >20,000 cells/uL will be summarized for each treatment group.

In addition, the change and percent change from baseline in complete blood count with Differential will be summarized for each treatment group.

The incidence of subjects with abnormalities for ALT/AST/ALP will be summarized overall and at each visit for each treatment group for the following categories:

$\geq 3 \times \text{ULN}$

$\geq 5 \times \text{ULN}$

Document: Statistical Analysis Plan

Author: [name]

Version Number: 1.1

Version Date: 18Jan2023

Template No.: CS_TP_BS016 Revision 5

Reference: CS_WI_BS005

Effective Date: 01Apr2018

$\geq 8 \times \text{ULN}$

The incidence of subjects with abnormalities for total bilirubin and conjugated bilirubin will be summarized overall and at each visit for each treatment group for the following categories:

$> 1 \times \text{upper limit of normal (ULN)}$

$\geq 2 \times \text{ULN}$

Shift Tables from Baseline to Worst Post-baseline CTCAE Grade are presented.

